##### Step 2: Draw 1000 mean imputation slopes for each treatment

Let  $\beta_T$  and  $\beta_P$  represent the true slopes in drug and placebo respectively with  $f(\beta_T) \sim N(\hat{\beta}_T, \hat{\sigma}_T^2)$  and with  $f(\beta_P) \sim N(\hat{\beta}_P, \hat{\sigma}_P^2)$ , using the slope (SE) estimates obtained in step 1. Draw 1000 random slopes from the appropriate distribution (see Section 11.3) for each treatment.

##### Step 3: Draw 1000 slopes for each subject

From the respective SE for each treatment slope from step 1, derive an approximation for the SD as  $SE \cdot \sqrt{n}$  where  $n$  is the number of subjects in the model randomized to the relevant treatment. For each mean imputation slope obtained in step 2, draw an individual slope for each subject randomized to the respective treatment from a normal distribution with mean equal to the mean imputation slope and relevant SD as derived above.

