8.3 Prohibited Medications including approved and non-approved medications for IPF

8.3.1 Medications approved for IPF

- Nintedanib
- Pirfenidone

Following the most recent DSMB recommendation, the above approved medications for IPF are prohibited in GALACTIC-1, and if taken, should result in immediate exclusion from screening for the study, or withdrawal from the study treatment.

Under caring physician's medical judgement, if deemed appropriate, patients with IPF may discontinue nintedanib or pirfenidone and be considered for screening after a wash out period of minimum 7 days.

Following randomization, study participants are only permitted to take nintedanib or pirfenidone after withdrawals of the inhaled study treatment.

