### 3.1 Sample Size Determination

In the original design, the planned 150 subjects per arm (randomized 1:1:1 to the 3 treatment arms) provided approximately 87% power to detect a true mean difference of 100 ml between treatment arms in the FVC decline at Week 52, assuming a between subject standard deviation of 280ml, based on a two-sided 5% significance level.

For the updated design, the randomization ratio was changed to 2:1 (GB0139 3mg: Placebo). To detect a difference from placebo in the decline of FVC of 100ml with a standard deviation of 240ml at the significance level of 10%, a sample size of 141 would give 75% power. The lower standard deviation in the updated design was based on a blinded review of the data.

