$\beta_3$  is the effect of treatment on the slope compared to Placebo

$\alpha$  and  $\gamma$  are elements of the intercept and slope respectively

$a_i$  and  $g_i$  are random specific components of the intercept and slope respectively for the ith patient, assumed to be normally distributed with mean 0 and arbitrary covariance matrix

	Plus-Project Statistical Analysis Plan	
	Protocol Number: GALACTIC-1	Version: 1

$FVCb_i$  is the baseline FVC (mL) for the  $i$ th patient

$\tau_k$  is the intercept coefficient of the effect of treatment  $k$  ( $k=1, 2$ )

$\beta_f$  is the effect of 1ml increase in the baseline FVC

$\varepsilon_{it}$  is the random error for  $i$ th patient at time  $t$  assumed to be independent and normally distributed with mean 0 and variance  $\sigma^2$

This approach adopts a missing at random (MAR) assumption (i.e., the probability of an observation being missing depends only on observed measurements). Subjects with missing data at a particular time point still contribute to the analysis at that time point based on their other observed data used in the model (i.e., treatment, baseline FVC, and the FVC at baseline). Data that remain unobserved due to ICEs will be handled as described above. Other missing data will be imputed within the regression model under the MAR assumption.

The linearity assumption for the rate of change in FVC from baseline to week 52 will be explored graphically. Graphical displays will be provided of the mean ( $\pm$  SEM) observed FVC and mean change from baseline for each treatment group by visit.

The assumptions of the analysis will be checked by inspection of graphical displays of the residuals.

A cumulative distribution plot of the percentage of subjects by change from baseline in FVC in mL at week 52 will be presented.

The primary analysis detailed above will be repeated for the Primary Population, PP Analysis Set and for SoC1 / Combination and SoC2 / Monotherapy Populations (only for the mITT Analysis Set).

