### 11.3 Primary Estimand Sensitivity and Tipping Point Analyses

A sensitivity analysis to test the robustness of the MAR assumption used in the main estimand analysis will be performed to assess the results with missing Week 52 FVC data.

Non-monotone missing data or missing data at other visits before week 52 will not be imputed. Multiple imputation will be used to handle missing data at week 52. The imputation model will be similar to the statistical model of the primary analysis.

For the imputation of week 52 data that is not available for reasons other than the occurrence of an ICE, the imputation model will be run on the subset of patients who prematurely discontinued trial drug but have been followed up for FVC measurements at week 52. FVC measurements that remain unobserved due to ICEs will still be handled as described in Section 7.2.1. Table 5 below contrasts the MAR approach used in the main estimand analysis with the MNAR approach used in the sensitivity analysis.

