**Table 5 – Missing Data Approaches**

Analysis	No FVC result but alive at Week 52	
	Handling of missing FVC result	Underlying assumption
Primary Estimand Analysis	Missing data handled by model.	Assumes missing at random. Discontinued subjects would have behaved similarly to subjects who did not discontinue who are in the same treatment group.
Sensitivity analysis	Based on the slope estimates for GB0139 dose and placebo among subjects who experience ICE without missing FVC data.	Subjects with a missing result would have behaved similarly to discontinued subjects with a result who are in the same treatment group.

The slope (SE) estimates of both treatment groups will be used in the sensitivity analysis. This approach is considered appropriate since the reasons for trial drug termination are expected to be similar between subjects with and without missing FVC data (discontinuation mainly due to AEs). The Sensitivity analysis corresponds to the assumption that in subjects with missing FVC data, the treatment effect would have persisted in the same manner as for subjects without missing FVC after trial drug discontinuation.

The number of imputations will be set to 1000 in order to ensure adequate efficiency for the estimation of missing data. For each imputed dataset, the same statistical model as defined for

	Plus-Project Statistical Analysis Plan	
	Protocol Number: GALACTIC-1	Version: 1

the primary analysis will be used for the analysis. See Section 7.2.1 for a description of the primary analysis model. The results will be pooled following the standard multiple imputation procedure. See Section 11.4 for further information on the implementation of the multiple imputation approach.

If the primary analysis and sensitivity analysis reach differing conclusions a tipping point analysis will be done. The tipping point analysis will be performed by applying an incremental shift from the imputed FVC value generated under MAR assumption toward the imputed FVC value generated under the MNAR assumption. The value of the shift that overturns the primary analysis result will represent the tipping point.

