##### Step 4: Impute any monotonic missing FVC data at 52 weeks using each slope

- a) Considering that the withdrawal of a subject leading to missing data can occur at any time during the study, the timepoint of the last available FVC value has to be taken into account to impute the missing FVC value at 52 weeks:
- b)  $FVC_{week\ 52\ imputed_{ij}} = \text{last FVC value available}_i + \hat{\beta}_{ij} * (\text{time between date of last FVC value available } i \text{ and planned 52 week timepoint [days]})$

	Plus-Project Statistical Analysis Plan	
	Protocol Number: GALACTIC-1	Version: 1

where  $i$  denotes the indicator of the  $i$ th subject,  $j$  the indicator of the  $j$ th imputation and  $\beta_{ij}^{\wedge}$  denotes a random slope sampled from the distribution mentioned above for the  $i$ -th subject in the  $j$ -th imputation.

- c) Create 1000 imputed FVC datasets for subjects with monotonic missing FVC data at 52 weeks including replicates of any FVC data collected in the study with the addition of the imputation specific 52 week result.
- d) Create 1000 identical FVC datasets for subjects with no monotonic missing FVC data at 52 weeks.
- e) Combine data from b and c.

Step 5: Run primary analysis model on each imputed dataset

Run the model of the primary analysis on each imputed dataset, using a "by \_IMPUTATION\_" statement to obtain 1000 parameter estimates (variable = estimate) and standard errors (variable = stderr).

Step 6: Combine the results obtained in step 4 using PROC MIANALYZE

```
Ods output ParameterEstimates=step5;
Proc Mianalyze data=step5 ;
modeffects estimate;
stderr stderr;
Run;
```

	Plus-Project Statistical Analysis Plan	
	Protocol Number: GALACTIC-1	Version: 1

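### The Week 52 multiple-imputation check does not use each leaver's own fitted FVC trajectory, so it can differ from the primary analysis even when missing at random holds

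*SAP*

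**What the plan says.** SAP 7.2.2 fits a random-coefficient model to change from baseline in FVC. It contains terms that "are random specific components of the intercept and slope respectively for the ith patient", independent within-subject errors, and a MAR assumption under which missingness may depend on observed values. A leaver's own FVC history therefore informs the fit.

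For the check on MAR, SAP 11.3 states: "The imputation model will be similar to the statistical model of the primary analysis". It adds that the imputation model is run on subjects who stopped trial drug early but were followed to Week 52, and Table 5 repeats this.

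The procedure itself is in SAP 11.4:

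- Step 1 takes one slope and SE per arm from the primary model on observed data, without naming the 11.3 subset. Step 2 draws mean slopes and refers back to 11.3.
- Step 3 tells the programmer to "draw an individual slope for each subject randomized to the respective treatment from a normal distribution with mean equal to the mean imputation slope", with SD approximated by SE times the square root of n.
- Step 4 notes that "the timepoint of the last available FVC value has to be taken into account to impute the missing FVC value at 52 weeks". It then sets Week 52 to the last FVC plus slope times the gap, which is given in days.
- Step 5 refits the primary model to each completed dataset.

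SAP 11.3 also says: "If the primary analysis and sensitivity analysis reach differing conclusions a tipping point analysis will be done". SAP 7.2.2.4 runs the multiple-imputation check only if the amount of missing data causes concern, and gives no threshold.

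**The concern.** Steps 3-4 depart from the primary model in three ways that have nothing to do with data being missing not at random (MNAR).

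1. The future slope is drawn around a group mean. Nothing in the draw reflects how fast that subject has been declining.
2. The last reading is carried forward with its measurement error and no new residual is drawn. The same error then sits at the last visit and again at Week 52, the time point with most leverage on the slope, while Step 5 assumes the two errors are independent.
3. SE times root n contains measurement error as well as between-subject slope variation, although the fitted model already estimates the latter separately.

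This is the only planned departure from MAR for living subjects with missing FVC, and a differing conclusion triggers the tipping-point analysis. That analysis shifts values away from a MAR imputation, but 11.4 gives no recipe for a MAR imputation other than these same steps, so its starting point need not match the primary result. If the check can disagree for reasons of construction, the reader cannot tell whether missing data threaten the result.

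**Working it through.** **The plan's own figure.** SAP 3.1 states, for a 100 mL difference and SD 240 mL: "at the significance level of 10%, a sample size of 141 would give 75% power". With 94 on GB0139 and 47 on placebo, SE = 240 × √(1/94 + 1/47) = 42.9. Then 100/42.9 = 2.33, and Φ(2.33 − 1.645) = 75.4%. The figure reproduces.

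**One leaver, worked by hand.** From the documents: placebo mean slope −200 mL/yr, SD 240 mL, post-baseline visits at Weeks 4, 8, 12, 26, 40 and 52. Assumed: 240 is the SD of fitted individual slopes; residual SD σ is 70, 100 or 150 mL; the baseline reading has the same error, shared by all changes from baseline.

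With time in years, the six visits give Σ(t − mean t)² = 0.682. The between-subject slope SD is then √(240² − σ²/0.682), which is 224, 207 and 157 mL/yr. Since SE × √n returns 240, the Step 3 draw is 7%, 16% and 53% wider than the slope variation it stands for.

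Take a placebo subject whose readings to Week 26 lie exactly on a 400 mL/yr decline, with nothing after.

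- SAP Steps 3-4: mean Week 52 change = −400 × 0.5 + (−200 × 0.5) = −300 mL; SD about 240 × 0.5 = 120 mL.
- Primary model: let V = σ_b²tt′ + σ²11′ + σ²I and c = σ_b²t + σ²1 for the four observed times, where σ_b is the slope SD and t is in years. The mean is −200 + c′V⁻¹(y + 200t) and the variance is σ_b² + 2σ² − c′V⁻¹c.

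| Residual SD | SAP mean (SD) | Primary model mean (SD) |
|---|---|---|
| 70 | −300 (120) | −336 (138) |
| 100 | −300 (120) | −301 (171) |
| 150 | −300 (120) | −261 (202) |

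The SAP value is too favourable when readings are precise, because the subject's own fast decline is ignored. It is too unfavourable when readings are noisy, because a low last reading is taken at face value. The means agree only where the two faults cancel; the spread agrees in none of the three cases.

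**Effect on the treatment difference.** In simulation, leaving depended only on observed FVC, so MAR held exactly. The true difference was 100 mL/yr and the primary model recovered it. Large-sample shifts from the primary estimate, with slopes from the whole arm (Step 1 as written):

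| Assumed slope SD / error SD | Same leaving rule in both arms | More leaving on 3 mg | More leaving on placebo |
|---|---|---|---|
| 150 / 130 | +2, +7 | −9 to −10 | +14 |
| 235 / 35 | −4 | +5 | −9 |
| 210 / 80 | within 2 | within 2 | within 2 |

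When leaving was unrelated to FVC there was no systematic shift. Imputation conditional on each subject's own data stayed within about 2 mL/yr throughout.

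- With decline-driven leaving in one arm only, at trial size, shifts were about 10-12 mL/yr at residual SD 70 and about 15-16 mL/yr in the opposite direction at 150, and near zero at 100.
- The widest whole-arm shift in any run was about 31 mL/yr.
- With slopes from followed-up discontinuers (11.3), one set moved by −3 to +6 mL/yr; the widest shift in any run was about 18. That subset is itself selected on decline: at slope SD 210 and error SD 80, its fitted slopes were −296 and −200 when the true arm slopes were −200 and −100.

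**Changed conclusions at the two-sided 10% level, N = 141.** The check and the primary analysis disagreed in about 2-9% of trials, against 0-5% with conditional imputation (64-150 trials per scenario, so imprecise). Under one-arm decline-driven leaving the rates were 6-16% against 0.4-4%. The primary SE was about 44 mL/yr.

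**Units.** The primary slope is per year (SAP 11.5.1), but Step 4b multiplies by days. From Day 183 to Day 365 is 182 days; unconverted, −200 × 182 = −36,400 mL. The simulations used years.

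**The case against.** The strongest reply is that the check is meant to disagree. Table 5 assumes that subjects with missing results behave like discontinued subjects with results in the same arm, so a group slope from followed-up discontinuers is part of the intended MNAR assumption. This stands: a group-based departure is not in itself an error, and some disagreement is by design. What it does not cover is the missing residual, the duplicated error, the spread of the draw, or the fact that 11.4 offers no version of the procedure that returns the primary result when there is no departure.

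It is also fair that Step 4 starts from the subject's own last FVC, so loss to date is kept and only the future slope ignores the subject's history. The SAP itself calls the SD an approximation.

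Four stronger readings are tempting, and the documents do not support them.

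- *The check is biased by a predictable amount.* The faults oppose each other, and the sign and size depend on a residual SD and a leaving rule that the documents do not give.
- *The primary result is compromised.* The check does not enter the primary estimate.
- *Decline is shown to drive missing FVC.* Protocol 8.3.1 says "study participants are only permitted to take nintedanib or pirfenidone after withdrawals of the inhaled study treatment", but that concerns stopping study drug. Protocol 6.2 and 10.5 let such participants stay for scheduled visits, and SAP 7.2.2 uses their later FVC. Decline-driven loss of FVC is plausible but remains an assumption.
- *Completers are dropped from the imputed data.* Step 4(e) reads "Combine data from b and c", while the completers' datasets are made in (d). Item (a) runs straight into the formula labelled (b), so the list appears to be lettered one step out. This is clerical.

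**Conclusion.** The point holds at moderate strength. As written, Steps 3-5 can differ from the primary analysis when MAR is exactly true, so disagreement cannot be read cleanly as evidence against MAR.

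Under the assumed leaving rules and residual SDs, the treatment difference shifts from near 0 to roughly 10-30 mL/yr with whole-arm slopes, and from near 0 to roughly 18 mL/yr with slopes from followed-up discontinuers. It is largest when decline-driven leaving is confined to one arm. When both arms leave by the same rule it is mostly under 5 and at most about 10 mL/yr. Even the widest shift is below one primary SE (31/44 = 0.70). The consequence is limited to how a conditional robustness check, and the tipping-point analysis that follows it, can be interpreted. It is worth correcting before database lock.

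**What to change.** Replace Steps 3-4 as follows.

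1. For each imputation, draw the fixed effects. Then draw the subject's intercept and slope from the fitted primary model conditional on that subject's observed FVC, using the model's between-subject and residual variances.
2. Draw Week 52 FVC from that trajectory and add a new residual.
3. Keep the stated MNAR assumption, but apply it as an explicit change in slope after the last observed FVC. Estimate it from the post-discontinuation FVC of followed-up discontinuers in the same arm. Zero departure then reproduces the primary MAR result, apart from simulation error, and the tipping-point shift starts there.
4. Make Step 1 name the 11.3 subset, put slope and gap in Step 4b in the same unit, and correct the lettering in Step 4(e).

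The cost is some SAP rewording and slightly more programming, with no new data. The drawback is that the departure will be imprecisely estimated if few discontinuers are followed up; the tipping-point analysis would then carry more of the weight.

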##### Step 4: Impute any monotonic missing FVC data at 52 weeks using each slope

- a) Considering that the withdrawal of a subject leading to missing data can occur at any time during the study, the timepoint of the last available FVC value has to be taken into account to impute the missing FVC value at 52 weeks:
- b)  $FVC_{week\ 52\ imputed_{ij}} = \text{last FVC value available}_i + \hat{\beta}_{ij} * (\text{time between date of last FVC value available } i \text{ and planned 52 week timepoint [days]})$

	Plus-Project Statistical Analysis Plan	
	Protocol Number: GALACTIC-1	Version: 1

where  $i$  denotes the indicator of the  $i$ th subject,  $j$  the indicator of the  $j$ th imputation and  $\beta_{ij}^{\wedge}$  denotes a random slope sampled from the distribution mentioned above for the  $i$ -th subject in the  $j$ -th imputation.

- c) Create 1000 imputed FVC datasets for subjects with monotonic missing FVC data at 52 weeks including replicates of any FVC data collected in the study with the addition of the imputation specific 52 week result.
- d) Create 1000 identical FVC datasets for subjects with no monotonic missing FVC data at 52 weeks.
- e) Combine data from b and c.

Step 5: Run primary analysis model on each imputed dataset

Run the model of the primary analysis on each imputed dataset, using a "by \_IMPUTATION\_" statement to obtain 1000 parameter estimates (variable = estimate) and standard errors (variable = stderr).

Step 6: Combine the results obtained in step 4 using PROC MIANALYZE

```
Ods output ParameterEstimates=step5;
Proc Mianalyze data=step5 ;
modeffects estimate;
stderr stderr;
Run;
```

	Plus-Project Statistical Analysis Plan	
	Protocol Number: GALACTIC-1	Version: 1

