### 7.2.1 Primary Efficacy Endpoint Analysis

The primary efficacy endpoint is the annual rate of decline in Forced Vital Capacity (FVC; expressed in mL over 52 weeks). Spirometry data provided by an external vendor showing the FVC (L) will be multiplied by 1000 to convert to mL. The analyses will be based on all FVC values obtained. Any FVC values post Day 453 will be omitted from the analyses.

The primary efficacy endpoint will be analyzed according to the estimand framework. Strategies for handling FVC data affected by the inter-current events (ICEs) of death, treatment discontinuation, and initiation of additional IPF therapy (pirfenidone or nintedanib) will be employed. Full details regarding use and imputation of FVC data in relation to ICEs are given in the next section.

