### 7.2.2 Main Estimand and Analysis

The primary analysis will test for superiority of GB0139 3mg compared to Placebo (Plc) for the annual rate of decline in FVC in mL over 52 weeks in subjects not receiving pirfenidone or nintedanib at baseline in the mITT Set. The main estimand for the primary efficacy endpoint is as follows:

- Population: Primary Population, mITT set.
- Variable of interest: Change from baseline in FVC in mL over 52 weeks
- Intercurrent events:
  - Death: FVC attributed the lowest value recorded in the trial when a patient dies

	Plus-Project Statistical Analysis Plan	
	Protocol Number: GALACTIC-1	Version: 1

- Treatment Discontinuation: Analysis will include any FVC measurements after randomised treatment discontinuation
- Initiation of additional IPF therapy (nintedanib or pirfenidone): Analysis will include any FVC measurements after initiation of additional IPF therapy
- Summary measure: Comparison of slopes assessed through the treatment by time interaction.

The null hypothesis is:

$H_0$ : There is no difference in the annual rate of decline in FVC in mL between GB0139 3mg and Plc

The alternative hypothesis is:

$H_a$  : There is a difference in the annual rate of decline in FVC in mL between GB0139 3mg and Plc

A restricted maximum likelihood (REML) approach will be used, with a random coefficient regression (random slopes and intercepts) model fitted to test the hypotheses. The decrease in FVC is assumed to be linear within each subject over 52 weeks [5].

Baseline FVC and time will be fitted as continuous covariates. The treatment group and the interaction term for time by treatment group will be added as fixed effects. Random subject intercept and time effects will be fitted and will be assumed to be normally distributed with arbitrary covariance matrix. The within-subject errors will be assumed to be independent and normally distributed with mean zero and a common variance. The Kenward-Roger approximation will be used to estimate denominators degrees of freedom.

The statistical model will be as follows:

$$Y_{itk} = (\alpha + a_i + \tau_k) + \beta_f FVCb_i + (\gamma + \beta_3 T_3 + g_i) t + \varepsilon_{it}$$

where:

$Y_{itk}$  is the change from baseline measured for ith patient at time t (actual time) in treatment group k

$t$  is the time since randomization in years

$T_3 = 1$  if the subject is in the GB0139 3mg group, otherwise  $T_3 = 0$

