#### **11.4 Multiple Imputation Procedure**

The following steps provide guidance on how missing FVC data at week 52 will be implemented using multiple imputation to allow sensitivity analyses of the primary endpoint. Refer to Section 11.3 for the description of the sensitivity analyses regarding handling of missing data.

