##### Step 1: Run Primary Analysis Model on Observed Data

Run the primary analysis model to get the slope estimates with standard errors (SE) for each treatment group. Let  $\hat{\beta}_T$  and  $\hat{\sigma}_T$  denote the slope and SE estimates in treatment group GB0139 3mg and  $\hat{\beta}_P$  and  $\hat{\sigma}_P$  the slope and SE estimates for placebo.

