## 11.5 SAS Code

### 11.5.1 Primary analysis

```
ods output estimates=tests tests3=fixed;
proc mixed data=adef;
  where paramcd='FVC';
  class subjid trt01pn;
  model cfb = base areltn trt01pn trt01pn*areltn /ddfm=kr s residual outp=resplot;
  random intercept areltn / sub = subjid type = un;
  estimate 'Plc Slope' areltn 1 trt01pn*areltn 1 0/cl;
  estimate '3mg Slope' areltn 1 trt01pn*areltn 0 1/cl;
  estimate 'Slope 3mg v Plc' trt01pn*areltn 1 -1/cl;
run;
```

where

subjid = Subject ID

trt01pn = Randomized treatment group (1=Placebo, 2= GB0139 3mg)

base=Baseline FVC for the subject

areltn = Years since first dose

cfb = Change from baseline in FVC

<mean baseline FVC> = the mean of the variable base across all records in the dataset FVC relating to the population of interest (i.e. all records to be included in the model)

	Plus-Project Statistical Analysis Plan	
	Protocol Number: GALACTIC-1	Version: 1

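### SAP 11.4, Step 4b multiplies a slope in mL per year by a gap in days, so the imputed change to Week 52 is about 365 times too large if programmed as written

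*SAP*

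**What the plan says.** SAP 7.2.1 states that the spirometry values in litres "will be multiplied by 1000 to convert to mL". In the model equation of SAP 7.2.2 the time variable "is the time since randomization in years", and the SAS code in 11.5.1 defines its time variable the same way: "areltn = Years since first dose".

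SAP 11.4 introduces the imputation thus: "The following steps provide guidance on how missing FVC data at week 52 will be implemented using multiple imputation". Its steps are:

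- **Step 1:** "Run the primary analysis model to get the slope estimates with standard errors (SE) for each treatment group".
- **Step 2:** draw 1000 mean slopes per arm, "using the slope (SE) estimates obtained in step 1".
- **Step 3:** draw a slope for each subject around each mean slope. The SD is the SE times the square root of the number of subjects in the arm, and it starts "From the respective SE for each treatment slope from step 1".
- **Step 4b:** imputed Week 52 FVC equals the last available FVC plus the drawn subject slope times the time between the last FVC "and planned 52 week timepoint [days", with the unit given in square brackets.

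Section 11.3 says the imputation model is similar to the primary model. It also says that a tipping-point analysis follows if the sensitivity and primary analyses reach different conclusions.

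**The concern.** A slope per year has to be multiplied by a time in years. Step 4b multiplies it by a time in days, and no step between the model fit and that product rescales either quantity.

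The multiple imputation is the only analysis in the plan that relaxes the missing-at-random assumption for unobserved FVC. The supplementary analyses in SAP 7.2.2.3 vary the handling of death, treatment discontinuation and added IPF therapy. The repeated-measures model in 7.2.2.4 still relies on missing at random. The result of the imputation also decides whether the tipping-point analysis is run, and that analysis shifts imputed FVC values towards those produced under the not-at-random assumption. If the imputed values are meaningless, both robustness checks are lost.

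**Working it through.** The SAP gives no numerical result for this step, so there is no stated figure to reproduce. The check is of units, followed by an illustration at the planning values.

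**Units**

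- Response: mL (SAP 7.2.1). Model time: years (SAP 7.2.2 and 11.5.1). The Step 1 slopes and SEs are therefore in mL/year. The equation counts time from randomisation and the code from first dose, but Step 4b uses a difference between two dates, so the origin does not matter.
- Step 2 draws from a normal distribution with those slopes and SEs: still mL/year.
- Step 3 uses SD = SE × √n: still mL/year.
- Step 4b: imputed change = slope (mL/year) × gap (days). The product is not in mL.

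The consistent form is slope × gap / D, where D is the number of days per year. The ratio of the written form to the consistent form is D, that is 365 or 365.25, for every slope and gap. Fitting the model to the subset described in Section 11.3 instead of to all observed data leaves the slope unit, and so the ratio, unchanged.

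**Illustration**

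Inputs:

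- Placebo slope -200 mL/year (Protocol 2.1, sample size justification).
- 3 mg slope -200 + 100 = -100 mL/year, assuming the full planned difference of 100 mL.
- Scheduled days 85, 183, 281 and 365 (SAP Table 1).
- Smallest gap: Table 1 assigns FVC from Day 324 to Week 52, so a patient needing imputation has a last FVC no later than Day 323. The gap is then at least 365 - 323 = 42 days.

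The documents do not give D; 365.25 is used in the table.

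| Last FVC | Gap (days) | Placebo, as written (mL) | Placebo, gap in years (mL) | 3 mg, as written (mL) | 3 mg, gap in years (mL) |
|---|---|---|---|---|---|
| Day 323 | 42 | -8,400 | -23.0 | -4,200 | -11.5 |
| Day 281 (Week 40) | 84 | -16,800 | -46.0 | -8,400 | -23.0 |
| Day 183 (Week 26) | 182 | -36,400 | -99.7 | -18,200 | -49.8 |
| Day 85 (Week 12) | 280 | -56,000 | -153.3 | -28,000 | -76.7 |

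For example, at Week 26 on placebo: -200 × 182 = -36,400 as written, and -200 × 182 / 365.25 = -99.7. Using D = 365 changes the largest entry from -153.32 to -153.42 mL, about 0.1 mL.

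Even at the smallest gap, a patient with the mean planning slope would be imputed a negative FVC for any last value below 8,400 mL (placebo) or 4,200 mL (3 mg).

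The spread is inflated by the same factor. With the planning SD of 240 mL used as an illustrative slope SD in mL/year and a 182-day gap, the SD of the imputed change is 240 × 182 = 43,680 mL as written, against 240 × 182 / 365.25 = 119.6 mL.

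**The case against.** The strongest reply is that this will do little harm in practice. Section 11.4 presents its steps as guidance and gives no code for Step 4. The bracketed unit may only record how a difference of two dates is measured, with scaling left to the programmer. The slope unit is never stated in Section 11.4 and has to be inferred. Taken literally, the formula gives FVC values thousands of mL below zero, which anyone checking the output should see. Section 7.2.2.4 runs the analysis only if the amount of missing data causes concern, the tipping-point analysis needs a further trigger, and only patients with monotone missing Week 52 FVC receive imputed values. The mL figures rest on planning slopes, whereas Section 11.3 fits the imputation model to patients who stopped trial drug and still have a Week 52 FVC, for whom the documents give no slope.

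Most of this stands as to weight. A plausible but wrong conclusion is unlikely to slip through, and the tabulated values are illustrations. It does not rescue the formula. The bracketed unit sits inside the multiplied term, and Step 4b is the only rule given for the imputed value. Elsewhere the SAP writes its conversions out: litres to mL by 1000 in 7.2.1, and days to weeks by dividing by 7 in 7.2.3.3. Section 11.3 also states the analysis without the condition in 7.2.2.4.

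**Conclusion.** The concern holds. As written, Step 4b inflates the imputed change to Week 52, and its spread, by the number of days in a year. The factor follows from the SAP's own units and does not depend on the assumed slopes; only the mL examples do.

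The factor applies to the imputed change, not to the whole FVC value or the pooled treatment effect. The effect on the pooled estimate depends on how many patients lack a Week 52 value and in which arm, and it was not computed. The error is confined to the multiple-imputation sensitivity analysis and the tipping-point analysis that depends on it. It should be corrected, but it does not threaten the primary result.

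**What to change.** In SAP 11.4, Step 4b, express the gap in years: the days from the last available FVC to the planned Week 52 timepoint, divided by the days-per-year constant used to derive areltn. State that constant in the SAP so that model and imputation share one time scale.

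The cost is one unit conversion in one formula, with no new data and no change to the primary analysis. It should be made and documented before database lock. The blinded data review meeting in SAP 4.6 already allows SAP actions to be agreed.

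With the conversion, the placebo examples above fall between -23.0 and -153.3 mL, which is consistent with the planned decline of 200 mL per year.
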